### ***Metabolic measures***

*Fuel utilisation:* Breath-by-breath changes in pulmonary gas exchange and ventilation will be non-invasively measured at rest to enable the estimation of resting metabolic rate (RMR). The assessment of pulmonary gas exchange (e.g.  $V_{O_2}$  and  $V_{CO_2}$ ) will give us the respiratory exchange ratio (RER). RER is a reliable and valid measure of fuel utilisation. To assess RMR, participants will be asked to lie down and rest for 15 mins, following this, pulmonary gas exchange will be measured via a gas analysis system for 5 min. Participants will be required to use a mask covering their nose and mouth (no restriction to breathing). In order to assess inspired and expired gas (volume and concentration), gases will be sampled through a capillary line attached to the turbine inside the face mask. A sub analysis of this breath by breath data will give us the respiratory exchange ratio (a value of 0.7 indicates only fatty acid metabolism and values of > 1 indicates only glucose metabolism, any value in the middle equates to a combination of both). This is an accurate assessment of rate of energy expenditure and fuel utilisation, and will be indicative of what proportion of carbohydrate and fat is being metabolised [67]. In order to calculate the RMR and rate of carbohydrate, and fat metabolism the ISO 8996 equations will be used [68]. Pulmonary gas analysis will be performed on all testing visits. Calibration will follow the guidelines given in the user manual produced by COSMED Omnia. Briefly, this involves calibrating the gas analyser by passing through a sample of gas with a known concentration and calibrating the volume on the gas flowmeter by using a 3 L syringe to pass a known volume of air through the flowmeter.

### ***Cardiovascular measures***

*Macrovascular function:* Brachial artery FMD will be used as a measure of endothelial function [69]. Endothelial-dependent function is assessed by measuring FMD in response to a 5 minute ischaemic stimulus, induced by forearm cuff inflation [69]. Measurements will be performed in the supine position on the right arm with the cuff placed distal to the olecranon process. High-resolution duplex ultrasound (SonoSite Edge II, Bothell, Washington, USA) with a 12-MHz multifrequency linear array probe will be used to image the brachial artery at the distal

third of the upper arm and simultaneously record the longitudinal B-mode image and Doppler blood velocity trace. The angle of Doppler insonation will be 60°. Images will be optimized, and settings (depth, focus position, and gain) will be maintained between FMD assessments within each individual visit, and the location of the transducer will be recorded and marked on the skin using an indelible marker. Following a 60-s baseline recording period, the cuff will be rapidly inflated to 220 mmHg and maintained for 5 min (moorVMS-PRES, Axminster, UK). Ultrasound recordings will resume 30 s before rapid cuff deflation (<2 s) and be continued for 3 min thereafter in accordance with recommendations [66, 67]. All ultrasound scans will be performed by a member of the UoP research team (same researcher within participant). Analysis of brachial artery diameter will be performed using custom designed edge-detection and wall-tracking software, which is largely independent of investigator bias. Recent papers describe the analysis approach in detail [66, 67]. Briefly, from recordings of the synchronised artery diameter and blood velocity data, blood flow (the product of lumen cross- sectional area and Doppler velocity) will be calculated at 30 Hz. Shear rate (an estimate of shear stress independent of viscosity) will be calculated as four times the mean blood velocity/vessel diameter via commercially available software.

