## 2. SYNOPSIS

Study Title	The Effect of Chronic Passive Heating on Insulin Sensitivity and Cardiovascular function in People with Type 2 Diabetes Mellitus: A pre- and post-test trial.
Internal ref. no.	n/a
Problem statement	
Type 2 diabetes mellitus (T2DM) is a metabolic condition characterized by chronic hyperglycemia and progressive insulin resistance, which progressively lead to macro- and microvascular damage and subsequent impairments in blood pressure (BP) control. Therapeutic approaches to manage T2DM focus on improving glycaemic control and BP and include pharmaceutical treatments (e.g. Metformin and insulin), physical activity and exercise, and calorie restriction. However, pharmaceutical interventions can be expensive and are associated with low adherence. Although exercise and diet programs have been shown to be effective, like pharmaceutical interventions, they often have poor adherence in people with T2DM. With the number of people with T2DM (464 million) continuing to rise and expected to reach 700 million by 2045, the costs associated with the clinical management of this condition are likely to become unsustainable. There is, therefore, a need to explore the potential of alternative interventions. In particular, interventions which may be cheaper than clinical management and have better adherence than exercise, and hypoglycemic agents, to improve glycemic control and deleterious cardiovascular manifestations of this condition.

	Passive heating may be one such intervention with therapeutic potential.
Research question / hypothesis	
Before passive heating can be considered as a therapeutic option for improving metabolic and cardiovascular health in individuals with T2DM, we need to explore whether their chronic passive heating (1h x 10 days) is able to improve:
 
 
1) insulin sensitivity
 
2) glycaemic control
 
3) metabolic efficiency
 
4) vascular health
 

Study Design	We plan to run a within-subject, pre-, post-intervention study
Study Participants	Adults $\geq$ 35 years (post-menopausal for females), diagnosed with T2DM as defined by the world health organisation (WHO).
Planned Sample Size	We aim to recruit 20 individuals with T2DM.
Follow-up duration	7 days
Planned Study Period	18 months

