#### 10.4 Randomisation

Due to study design, randomisation will not be necessary.

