flow responses will be expressed as CVC (CVC = skin flux/MAP;  $\text{flux mmHg}^{-1}$ ). The average skin blood flow for both ACh and insulin will be calculated over the final 20 s of the intervals between each successful pulse (i.e. 100-120 s post each pulse) [71]. Maximal skin blood flow, taken at the highest point which will not always be following the final pulse and area under the curve (AUC) will be calculated for each participant. Skin temperature ( $T_{sk}$ ) will be recorded with skin thermistors (Grants Instruments, Cambridge) placed next to the Perspex chambers. BP will be measured on the contra-lateral arm to the site of iontophoresis using an automated BP monitor (Omron M5, Omron, Milton Keynes, UK) before and after each iontophoresis protocol to calculate mean arterial pressure (MAP).

*ECG:* HR will be automatically calculated from the ECG (Dynascope, Fukuda Denshi, Japan). Heart rate variability (HRV) will be calculated as a low frequency (LF) variable and root mean square of successive differences (RMSSD). LF has been chosen as it indicates a physiological origin of both sympathetic and vagal activity. RMSSD is then being calculated additionally as it gives a stronger representation of vagal tone (due to it being affected much less by respiratory sinus arrhythmia (RSA)) than LF thus improving validity of the vagal tone measure [72]. Both measures will be calculated from an ECG trace (Kubios HRV software, Kubios, Finland).

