### 11.3 Accountability of the Study Treatment

Due to the nature of the study, blinding of the participants will be impossible.

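### No provision for masking readers to visit when FMD, laser-Doppler and HRV values are derived from recordings in an open, single-group pre/post trial

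*Combined protocol and SAP*

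**What the plan says.** **Design.** The synopsis states: "We plan to run a within-subject, pre-, post-intervention study". Section 10.4 adds: "Due to study design, randomisation will not be necessary". There is one group and no concurrent control.

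**Blinding.** The only statement is in section 11.3: "Due to the nature of the study, blinding of the participants will be impossible". Scanners, readers and analysts are not mentioned there, in section 10.6 or in section 14. Section 14.4 says that no further analysis plan is needed. The contents list shows no section on masking.

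**How the values are obtained (section 10.6).**
- FMD: one member of the university research team scans a given participant at both visits. Diameter is then analysed from the recordings with software that detects and tracks the vessel wall, "which is largely independent of investigator bias".
- Laser-Doppler: signals are recorded in LabChart. Average flow is taken over a fixed window, 100 to 120 s after each pulse. Maximal flow is "taken at the highest point which will not always be following the final pulse", and an area under the curve is also calculated.
- HRV: the low-frequency measure and RMSSD are calculated from an ECG trace in Kubios.

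Macrovascular function, microvascular function and HRV are three of the 19 secondary outcomes in section 7.2. The test is a paired t-test or Wilcoxon signed-rank test at P < 0.05 (14.2).

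**The concern.** In an open pre/post study, a person who knows which recording came from after the intervention may read it, without intending to, in the hoped-for direction. The plan meets this risk only for FMD diameter, with software that it calls largely rather than wholly free of investigator influence. It offers no equivalent for laser-Doppler or HRV.

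The design makes this matter more. In a controlled trial, a reading habit that depended only on visit would affect both arms and cancel in the comparison. Here nothing cancels it. At stake is the credibility of the results under the vascular health objective, one of three secondary objectives, and of the HRV result, which is autonomic rather than vascular.

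**Working it through.** **Step 1: what each reading step fixes and what it leaves open.**

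| Measure | Fixed by the plan | Not fixed by the plan |
|---|---|---|
| FMD | Edge-detection and wall-tracking software; same scanner within participant | Selection of frames and of the peak |
| Laser-Doppler average | 100 to 120 s window after each pulse | Meaning of a successful pulse |
| Laser-Doppler maximum | It is the highest point | Artefact rule |
| HRV | Software and the two indices | Segment of trace; beat editing |

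For FMD, section 10.6 refers the reader to references 66 and 67 for the analysis method. In the reference list these are a sodium butyrate study and an indirect calorimeter study. FMD papers stand at 69 and 70, so this may be a numbering slip, but as printed the method cannot be traced.

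**Step 2: how a reading shift enters the estimate.** Let Δ be the true mean change and β the systematic difference between post and pre readings that comes from the reader.
- Single group: expected mean change = Δ + β.
- Two arms: expected difference in mean changes = (Δ₁ − Δ₀) + (β₁ − β₀), and the second term is zero if the habit is the same in both arms.

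With one group, β is carried over one for one.

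**Step 3: illustration of size.** The documents give no figure for β, so the shifts below are assumptions. Inputs from the plan are n = 15 (section 9) and a two-sided 0.05 level (sections 9 and 14.2).

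Let b = β divided by the SD of the paired change, and set Δ = 0. The chance of P < 0.05 is P(|T| > t*), where T is noncentral t with n − 1 degrees of freedom and noncentrality b√n. For n = 15, t* = 2.145 and √15 = 3.873. For n = 20 (everyone recruited completes), t* = 2.093 and √20 = 4.472.

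| Assumed b | b√15 | n = 15 | n = 20 |
|---|---|---|---|
| 0 | 0 | 5.0% | 5.0% |
| 0.05 | 0.194 | 5.4% | 5.5% |
| 0.10 | 0.387 | 6.5% | 7.1% |
| 0.25 | 0.968 | 14.7% | 18.6% |
| 0.50 | 1.936 | 43.8% | 56.5% |

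A larger sample makes a fixed shift more likely to reach significance, not less.

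**The plan's own figure.** Section 9 gives n = 15 for a 1 SD change in insulin sensitivity at 80% power. A paired t-test on the SD of the change needs 10, and 15 gives 94.9% power, so 15 is not reproduced on that reading. That is a separate matter: here 15 serves only as the number analysed.

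**The case against.** Much of the derivation is mechanical. FMD diameter is tracked by software, the skin-flow average has a fixed window, a maximum and an area are arithmetic, and the HRV indices come out of a package. One scanner per participant removes between-scanner variation. This stands: the room for judgement is limited and any bias is probably modest. The lower rows of assumed shifts (0 to 0.10 SD) may be the relevant ones, and there the false-positive rate moves little.

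Several stronger readings might be inferred and are not supported.
- *Readers are unmasked, or those who run the heating also read the files.* The plan is silent on both. Sections 10.5 and 11.1 do not say who delivers the heating, and section 10.6 does not say who derives the values. That reading takes place after the visit is itself inferred from the use of recordings.
- *The reader decides which pulses count or picks the peak by eye.* The text applies its window to each pulse, and the word successful may be a slip for successive. The highest point is defined as a maximum. What is shown is a missing definition and a missing artefact rule.
- *Frames are chosen or beats edited by hand.* The plan describes neither step. The point is only that it sets no rule for them.
- *The bias has been measured.* The percentages follow from assumed shifts and would be the same for a bias from any source.
- *The main result is at risk.* Insulin sensitivity is calculated from plasma glucose and insulin and is not exposed.

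What remains is that masking to visit is not provided for, the one named safeguard covers one measure and is partial, and the design has no control group to absorb an error.

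**Conclusion.** The gap is real but limited. The plan does not provide for masking readers to visit for three secondary outcomes, and in a single-group design any systematic reading shift goes in full into the reported change. With no true effect and 15 participants, the false-positive rate would run from 5.0% with no shift to 14.7% at 0.25 SD and 43.8% at 0.5 SD.

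The calculation assumes a paired t-test, normally distributed changes and the same average shift across participants. It says how sensitive the design is, not how large the bias will be. The change should be made because it is cheap and has to be in place before reading starts: values already read with the visit known can be repaired only by reading them again.

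**What to change.** Add to sections 10.6 and 14.2:

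1. A team member who does not read the modality concerned replaces participant and visit labels on the FMD, laser-Doppler and ECG files with random codes.
2. Files are read in random order, so that pre and post recordings are not handled as a known pair.
3. Reading rules are fixed beforehand: FMD frame and peak selection, the artefact rule for peak skin flow, what counts as a successful pulse (or correct the word), and the segment and beat-editing rule for HRV.
4. All values for both visits are locked before the code is opened.

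Correct the two FMD analysis citations at the same time.

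The cost is a small amount of file handling by existing staff, with no extra visits, participants or equipment. The report should also state the limit of this change: it removes reader bias only. Bias from an unmasked scanner, time effects, regression to the mean and participant expectation all remain.

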#### *Microvascular function:*

Individuals will be acclimated for a minimum of 30 minutes in an ambient temperature of 23 °C prior to acetylcholine (ACh) and insulin being delivered transdermally via iontophoresis to volar aspect of the left forearm as previously described [71].

Briefly, following cleaning of the skin surface with water for injection, two perspex rings will be attached to the skin with one acting as an anode, and the other as the cathode. These electrodes will be connected to the iontophoresis controller (MIC 2, Moor Instruments, UK). Both chambers have an 8 mm inner diameter. The anode chamber will be filled with ~ 0.5 mL of ACh (Braun, Melsungen, Germany), with a 1% concentration dissolved in water for injection. The cathode chamber will be filled with ~ 0.5 mL of insulin (Sigma-aldrich, Missouri, USA) with a 0.01% concentration dissolved in water for injection. The protocol for electrical pulses included: four at 25 µA, followed by a single pulse of 50 µA, 100 µA, 150 µA and 200 µA. These pulses will last for 20 s with 120 s intervals between each pulse where no current will be applied. An interval of five minutes will be given between testing each site (forearm, finger and foot).

Laser doppler probes (VP1T / 7, Moor Instruments, UK), connected to a perfusion monitor (moor VMS-LDF, Moor Instruments, UK) will be used to assess skin blood flow. Data will be recorded using an acquisition system (Powerlab, AD Instruments, Australia) and software (LabChart 7, AD Instruments, Australia). The laser doppler probes will be secured in the Perspex rings prior to the iontophoresis protocol on the forearm and on the corresponding site on the contra-lateral limb (to differentiate between local and systemic responses). Skin blood

flow responses will be expressed as CVC (CVC = skin flux/MAP;  $\text{flux mmHg}^{-1}$ ). The average skin blood flow for both ACh and insulin will be calculated over the final 20 s of the intervals between each successful pulse (i.e. 100-120 s post each pulse) [71]. Maximal skin blood flow, taken at the highest point which will not always be following the final pulse and area under the curve (AUC) will be calculated for each participant. Skin temperature ( $T_{sk}$ ) will be recorded with skin thermistors (Grants Instruments, Cambridge) placed next to the Perspex chambers. BP will be measured on the contra-lateral arm to the site of iontophoresis using an automated BP monitor (Omron M5, Omron, Milton Keynes, UK) before and after each iontophoresis protocol to calculate mean arterial pressure (MAP).

*ECG:* HR will be automatically calculated from the ECG (Dynascope, Fukuda Denshi, Japan). Heart rate variability (HRV) will be calculated as a low frequency (LF) variable and root mean square of successive differences (RMSSD). LF has been chosen as it indicates a physiological origin of both sympathetic and vagal activity. RMSSD is then being calculated additionally as it gives a stronger representation of vagal tone (due to it being affected much less by respiratory sinus arrhythmia (RSA)) than LF thus improving validity of the vagal tone measure [72]. Both measures will be calculated from an ECG trace (Kubios HRV software, Kubios, Finland).

### ***Other measures***

*Central haemodynamics:* Using thoracic bio-reactance technology (Physioflow), which will derive heart rate, stroke volume, cardiac output and total peripheral resistance, at rest. Four electrodes are placed on the participant's chest between which a small, painless current is passed.

#### **10.7 Discontinuation/Withdrawal of Participants from Study Treatment**

Participants may be withdrawn from the study if they ask to withdraw; if participant safety is in question; or if the study is stopped early.

## 10.8 Definition of End of Study

The end of study will be the date of the last visit of the last participant.

## **11. INTERVENTIONS**

### 11.1 Description of Study Intervention / Treatment

*Daily passive heating:* Participants will attend the laboratory on 8-12 occasions within a period of 14 days (~ 90 min per visit) with the aim of completing 10, at any point in the day. Anyone completing less than 8 will be excluded from analysis. During each visit participants will self-insert a rectal thermistor and will then be immersed into a hot tub (~ 40 °C) for 60 min. Body position will be manipulated as required to achieve and maintain a target  $T_{rec}$  at 38.5 °C using 40 °C water. Participants will be required to wear a bathing suit and a t-shirt for all heating visits.

### 11.2 Adherence to Study Treatment

The research coordinator will confirm that the participants have completed at least 8, 1 h passive heating sessions between experimental visits.

### 11.3 Accountability of the Study Treatment

Due to the nature of the study, blinding of the participants will be impossible.

### 11.4 Concomitant Medication / Therapies

Medication will be recorded on enrolment and updated throughout their time on the trial. For each experimental visit, hypoglycaemic aids will be stopped for the morning (see pre experimental instructions for details).

## **12. ASSESSMENT OF SAFETY (IF APPLICABLE)**

### 12.1 Definitions

A serious adverse event is any untoward medical occurrence that:

- Results in death,
- Is life-threatening,

NOTE: The term "life-threatening" in the definition of "serious" refers to an event in which the participant was at risk of death at the time of the event; it does not refer to an event which hypothetically might have caused death if it were more severe.

- Requires inpatient hospitalisation or prolongation of existing hospitalisation,
- Results in persistent or significant disability/incapacity, or

- Is a congenital anomaly/birth defect.
- Other important medical events\*

\*Other events that may not result in death, are not life threatening, or do not require hospitalisation, may be considered a serious adverse event when, based upon appropriate medical judgement, the event may jeopardise the participant and may require medical or surgical intervention to prevent one of the outcomes listed above.

## 12.2 Reporting Procedures for Serious Adverse Events

A serious adverse event (SAE) occurring to participant should be reported to the REC that gave a favourable opinion of the study where in the opinion of the Chief Investigator the event was: ‘related’ – that is, it resulted from administration of any of the research procedures; and ‘unexpected’ – that is, the type of event is not listed in the protocol as an expected occurrence. Reports of related and unexpected SAEs should be submitted within 15 days of the Chief Investigator becoming aware of the event, using the NRES report of serious adverse event form (see NRES website).

## 12.3 Recording and Reporting Procedures for All Adverse Events

All adverse events will be recorded in participant file notes. Distinction between SAE and AE will be made by an independent medical officer. All SAE will be reported to the sponsor and the REC regardless of if it is related or not.

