#### 10.5 Study intervention

*Daily passive heating:* Participants will attend the laboratory on 8-12 occasions within a period of 14 days (~ 90 min per visit) with the aim of completing 10, at any point in the day. Anyone completing less than 8 will be excluded from analysis. During each visit participants will self-insert a rectal thermistor and will then be immersed into a hot tub (~ 40 °C) for 60 min. Body position will be manipulated as required to achieve and maintain a target  $T_{rec}$  at 38.5 °C using 40 °C water. Aural temperature will also be measured every 15 min for determination of

validity and time lag compared to  $T_{rec}$ , for possible use in future studies. BP will also be measured at 15 min intervals after passive heating in the first intervention visit to firstly, establish safety data on the protocol (i.e. to avoid syncope) and secondly, be used as a benchmark for recovery time in subsequent intervention visits. Participants will be required to wear a bathing suit and a t-shirt for all heating visits.

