# 13. DATA HANDLING AND RECORD KEEPING

## 13.1 Data Collection Forms

Visit 1 will act as a screening, consent and baseline assessment (~1 h). All measures for this visit will be stored in the clinical records folder (CRF). Separate forms will be prepared for; anthropometrics, medical history, screening (i.e. blood pressures etc) and blood markers. All paper copies will be stored in the CRF's.

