## 13.2 Data Management

All data will be double data entered into excel. Macro's will be used to check for anomalies and corrected. The participants will be identified by a study specific participants number and/or code in any database. The name and any other identifying detail will NOT be included in any study data electronic file. The chief investigator ([name]) is responsible for database maintenance and management.

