## **15. ETHICS**

NHS Local Research Ethics Committee (REC) approval will be obtained prior to commencement of the study. The REC, local NHS, research and development department and all site specific forms and participant identification centre forms will be forwarded to the R&D department at Queen Alexandra Hospital Portsmouth, prior to recruitment of participants. Written informed consent will be obtained from all participants. Insurance indemnity will be provided by the University of Portsmouth for this study.

Every effort has been made to keep the risks and discomforts to a minimum, with first aid cover and extensive screening procedures in place but there are some risks associated to taking part.

Not all volunteers will experience any or all of the risks stated below, but participants will be made aware of them.

The main burden to participants is a 12 h fasting period before their experimental visits. Participants will be asked to cease all hypoglycaemic agents on the morning of testing and will be instructed to bring them with them on the day. This is in line with a normal fasted OGTT typically used in clinics. Prior to leaving the laboratory, participants will be provided with lunch, they can take their tablets and blood sugars checked prior to leaving.

We will also be asking people with T2DM to be immersed in 40 °C water for all intervention visits. This may cause some discomfort which will be assessed with a thermal sensation and comfort scale. We will be measuring the core temperature via rectal thermistor and monitoring it closely at all times. Participants will be reminded that they are free to withdraw at any time point and will also be withdrawn and cooled if  $T_{rec}$  raises above 39°C (as stated in the school SAP's).

Participants will be asked to insert a rectal thermistor on 8-12 occasions (water immersions). This can be uncomfortable upon insertion; however, this is necessary for safety purposes. Participants will be provided with lubrication and instructions.

Other less burdensome tests will be performed such as:

Blood pressure; participants will feel a cuff squeeze their arm and this can be uncomfortable for a few moments. Blood samples taken via intravenous access can cause discomfort associated with insertion of the needle.

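### The only analysis set requires 8 or more immersions, so participants stopped early for safety fall outside it, and the 7-day follow-up matches no planned contact after the post visit

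*Combined protocol and SAP*

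**What the plan says.** **Recording.** Section 12.3 states that "All adverse events will be recorded in participant file notes". It adds that an independent medical officer separates serious from non-serious events, and that "All SAE will be reported to the sponsor and the REC regardless of if it is related or not". (Section 12.2 words the duty to report to the ethics committee more narrowly. That is a separate inconsistency.) Section 13.2 says "All data will be double data entered into excel", without saying whether file notes count as data.

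**Other safety data.** Section 10.5 takes blood pressure at 15-minute intervals after the first immersion, partly to "establish safety data on the protocol". Section 15 says of the hot water: "This may cause some discomfort which will be assessed with a thermal sensation and comfort scale".

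**Analysis set.** Section 14.1 defines one population: those with both the pre and post assessments and 8 or more immersions. Sections 10.5 and 11.1 say that people with fewer than 8 are left out of the analysis, without limiting this to efficacy.

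**Withdrawal.** Section 10.7 lists participant safety among the reasons. Section 15 adds rectal temperature above 39 °C and blood pressure at or above 180/100 mmHg, and names hypotension and loss of consciousness as risks.

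**Follow-up.** The synopsis gives "Follow-up duration 7 days", with no start point or purpose. Section 10.6 places the post assessment less than 72 h after the intervention. Section 10.8 says "The end of study will be the date of the last visit of the last participant".

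**The concern.** The study collects safety information and expects that some people may be stopped for safety, but the only group it defines for analysis is selected on having tolerated most of the programme. None of the 19 secondary outcomes in section 7.2 is a safety or tolerability outcome. Section 14 plans no table of adverse events, stopped immersions or withdrawals, and section 14.4 says no analysis plan is needed beyond that section. An author who wants to comment on tolerability therefore has only a completer set to use.

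This matters because section 6 says the results will help judge whether passive heating could become a treatment for type 2 diabetes, and section 4 already describes the team's acute heating work as well tolerated. A similar statement from this study is foreseeable. If it rests on people with 8 or more immersions, it omits those most likely to contradict it. Separately, without a stated collection window, events arising after the last visit may be recorded for some participants and not for others.

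**Working it through.** **1. Can a person stopped for safety be in the analysis set?** Entry needs at least 8 immersions and a post assessment. A person withdrawn after, say, the second immersion has neither, and no other set is defined. A person stopped after the eighth immersion who still attends the post assessment stays in. The loss therefore concerns early stops and those who miss the post visit.

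**2. How many could be lost within the plan's own allowance?** Section 9 gives 15 required and 20 starting. 20 − 15 = 5, and 5/20 = 25%. This is an allowance, not a formal cap, and the documents do not say what share of it would be for safety.

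**3. Illustration of the two denominators.** Assumptions: 20 people start heating; k are stopped early for safety and leave the set; nobody else is lost; no completer has such an event. Completers then show 0/(20 − k) and all treated show k/20. Intervals are exact (Clopper–Pearson) two-sided 95%. With zero events the upper limit is 1 − 0.025^(1/n); for n = 17 that is 1 − 0.025^(1/17) = 19.5%.

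| k | Completer set | 95% interval | All treated | 95% interval |
|---|---|---|---|---|
| 1 | 0/19 = 0% | 0 to 17.6% | 1/20 = 5% | 0.1 to 24.9% |
| 3 | 0/17 = 0% | 0 to 19.5% | 3/20 = 15% | 3.2 to 37.9% |
| 5 | 0/15 = 0% | 0 to 21.8% | 5/20 = 25% | 8.7 to 49.1% |

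The completer estimate is zero in every row, whatever k is. At k = 1 and k = 3 the completer interval still contains the all-treated rate; at k = 5 it does not. The fault is selection: the set removes the events by construction.

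**4. Follow-up.** The last scheduled contact is less than 72 h, that is 3 days, after the intervention. What the 7 days cover depends on a start point that the plan does not give:

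- From the last immersion: 7 − 3 = 4, so at least 4 days have no planned contact.
- From the post assessment: all 7 days have none.
- From the first immersion: the 7 days end within the heating period and say nothing about the time after it.

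No section describes a contact after the post assessment, and none says when adverse-event collection starts or stops.

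**5. Can stops be classified?** Section 7.1 says that above 39 °C the heating protocol is terminated. Section 15 says that the participant is withdrawn. The first can be read as ending one session, the second as ending participation. A count of stopped immersions and withdrawals needs these passages to be reconciled.

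**The case against.** The strongest reply is that no safety or tolerability result is planned, so none can be biased. Section 14.1 feeds the endpoint tests in 14.2, nothing says adverse-event reporting would use that set, and 12.3 records events in everyone. For a 20-person single-arm study without a safety objective, this is a reporting matter that leaves the primary conclusion untouched. Much of that stands. The bias is conditional on a summary being made on the defined set. But the exclusion is worded without limit in three places, it is the only set available, and blood pressure is collected expressly as safety data.

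A reader might also infer stronger things that the documents do not support:

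- **That adverse events go nowhere but file notes.** Serious events also go to the sponsor and the ethics committee, and section 15 refers to approved procedures for adverse events that are not in the document.
- **That there is no adverse-event form.** Section 13.1 says "Separate forms will be prepared for; anthropometrics, medical history, screening (i.e. blood pressures etc) and blood markers", but this follows a description of visit 1 and reads as a list for that visit. The comfort scale's absence from 10.5 and 11.1 is likewise missing detail only.
- **That follow-up stops at the last visit.** Section 10.8 ends the study; it does not set each participant's collection window.
- **That withdrawn participants have no further contact.** Section 10.7 is silent on this and does not rule it out.
- **That everyone who overheats leaves the analysis.** Sections 7.1 and 15 do not agree on this.

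**Conclusion.** The point holds in a limited form. As written, the 8-session rule removes from analysis the people who could not tolerate heating early on, and no other set exists on which to report them. Any tolerability statement based on that set is biased towards good tolerance. The size cannot be fixed from the documents. On the assumptions shown, the completer set reports 0% where the all-treated figure is 5%, 15% or 25%. The adverse-event window is not stated, and the synopsis's 7 days match no contact after the post assessment; at least 4 days are uncovered if the count starts at the last immersion, which is an assumption. This concerns the safety data only, not the estimate of insulin sensitivity, and is a cheap improvement worth making.

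**What to change.** - In 10.5, 11.1 and 14.1, state that the 8-session rule applies to the efficacy analysis only.
- In 14.1, add a descriptive safety set: everyone who starts at least one immersion.
- In 14.2, tabulate on that set the adverse events, stopped immersions and withdrawals with reasons, and the first-visit blood pressure after heating.
- In 12.3, state when adverse-event collection starts and ends, and reconcile this with the 7 days in the synopsis. One way is a closing phone call that includes withdrawn participants who agree to it.
- Reconcile sections 7.1 and 15 on what follows a rectal temperature above 39 °C, so that a stopped session can be told apart from a withdrawal.

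The cost is one descriptive table and one short call per participant, with the protocol amendment that this needs. No extra participants or laboratory visits are required, and the efficacy analysis does not change.
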